
pod will be discarded after use. The transmitter and receiver and glucose meter will be disinfected with a bleach solution and 70% isopropyl alcohol wipes to remove any disinfectant residue.

4. Genetic Testing N/A

A. Describe

- i. the types of future research to be conducted using the materials, specifying if immortalization of cell lines, whole exome or genome sequencing, genome wide association studies, or animal studies are planned
- ii. the plan for the collection of material or the conditions under which material will be received
- iii. the types of information about the donor/individual contributors that will be entered into a database
- iv. the methods to uphold confidentiality

B. What are the conditions or procedures for sharing of materials and/or distributing for future research projects?

C. Is widespread sharing of materials planned?

D. When and under what conditions will materials be stripped of all identifiers?

E. Can donor-subjects withdraw their materials at any time, and/or withdraw the identifiers that connect them to their materials?

- i. How will requests to withdraw materials be handled (e.g., material no longer identified: that is, anonymized) or material destroyed?

F. Describe the provisions for protection of participant privacy

G. Describe the methods for the security of storage and sharing of materials

5. Subject Population: Provide a detailed description of the types of human subjects who will be recruited into this study.

15 lean, healthy control subjects (BMI <25 kg/m²)

15 obese, non diabetic subjects (BMI > 30 kg/m²)

15 T2DM subjects who will be age and BMI-matched to obese, non-diabetic subjects

15 T1DM subjects who will be age and BMI matched to control, non-diabetic subjects.

6. Subject classification: Check off all classifications of subjects that will be specifically recruited for enrollment in the research project. Will subjects who may require additional safeguards or other considerations be enrolled in the study? If so, identify the population of subjects requiring special safeguards and provide a justification for their involvement.

 Children	 Healthy	 Fetal material, placenta, or dead fetus
 Non-English Speaking	 Prisoners	 Economically disadvantaged persons

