This is a pilot project. We estimate that a sample size of 15 subjects per group will provide 80% power to detect within group differences of 1.1 standard deviations. For changes in hunger ratings of liking, wanting and hunger we will have at least 80% power to detect between group differences across all glycemic conditions (i.e. main effect of group) of 1.0 standard deviation and within each condition of 1.25 standard deviations.

SECTION VI: RESEARCH INVOLVING DRUGS, BIOLOGICS, RADIOTRACERS, PLACEBOS AND DEVICES

N/A

A. DRUGS, BIOLOGICS and RADIOTRACERS

1. **Identification of Drug, Biologic or Radiotracer:** What is (are) the **name(s)** of the drug(s) biologic(s) or radiotracer(s) being used? Identify whether FDA approval has been granted and for what indication(s).

All protocols which utilize a drug, biologic or radiotracer **not** approved by, but regulated by, the FDA, or a radiotracer regulated by the RDRC, must provide the following information:

- a. What is the Investigational New Drug (IND) **number** assigned by the FDA?
- b. Who holds the IND?
- c. All protocols which utilize a radiotracer not approved by, but regulated by the FDA must provide the IND number: _____
Alternatively, use of the investigational radiotracer may be under RDRC/RSC oversight: (check if appropriate) _____

For all investigational radiotracers, attach a copy of the RDRC/RSC application (for radioisotopes used in the PET Center, PET Center personnel may complete this step)
Go to <http://rsc.med.yale.edu/login.asp?url=myApps.asp>. When you have logged in, complete the application and attach a copy to this submission.

Alternatively, an **exemption from IND filing requirements** may be sought for a clinical investigation of a drug product that is lawfully marketed in the United States. If there is no IND and an exemption is being sought, review the following categories and complete the category that applies (*and delete the inapplicable categories*):

Exempt Category 1

The clinical investigation of a drug product that is lawfully marketed in the United States can be exempt from IND regulations if all of the following are yes:

- i. The intention of the investigation is NOT to report to the FDA as a well-controlled study in support of a new indication for use or to be used to support any other significant change in the labeling for the drug. Yes No

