a. State how the PI, or named designee, ensures that an investigational device is used only in accordance with the research protocol approved by the HIC, and maintains control of the investigational device as follows:

Maintains appropriate records, including receipt of shipment, inventory at the site, dispensation or use by each participant, and final disposition and/or the return of the investigational device (or other disposal if applicable):

Documents pertinent information assigned to the investigational device (e.g., date, quantity, batch or serial number, expiration date if applicable, and unique code number):

Stores the investigational device according to the manufacturer's recommendations with respect to temperature, humidity, lighting, and other environmental considerations:

Ensures that the device is stored in a secure area with limited access in accordance with applicable regulatory requirements:

Distributes the investigational device to subjects enrolled in the IRB-approved protocol:

SECTION VII: RECRUITMENT/CONSENT AND ASSENT PROCEDURES

1.

Targeted Enrollment: Give the number of subjects:

a. targeted for enrollment at Yale for this protocol 60
 b. If this is a multi-site study, give the total number of subjects targeted across all sites

2.

Indicate recruitment methods below. Attach copies of any recruitment materials that will

be used.

 Flyers	 Internet/Web Postings	 Radio
 Posters	 Mass E-mail Solicitation	 Telephone
 Letter	 Departmental/Center Website	 Television
 Medical Record Review	 Departmental/Center Research Boards	 Newspaper
 Departmental/Center Newsletters	 Web-Based Clinical Trial Registries	
 YCCI Recruitment database	 Clinicaltrials.gov Registry (do not send materials to HIC)	
 Other (describe): Yale Diabetes Registry (HIC# 0911005973)		

3.

Recruitment Procedures:

a. Describe how potential subjects will be identified.

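### The stated power of at least 80% for a 1.0 SD main effect of group relies on averaging over glycemic conditions that this single-period study does not have; with one value per person, power is 75% for a pair of groups and 59–90% for the four-group test.

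*Combined protocol and SAP*

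**What the plan says.** Section V, item 12 (Statistical Considerations) describes the study as a pilot and gives three power figures:

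- Within group: "15 subjects per group will provide 80% power to detect within group differences of 1.1 standard deviations".
- Between groups, averaged: "we will have at least 80% power to detect between group differences", specified as "between group differences across all glycemic conditions (i.e. main effect of group) of 1.0 standard deviation".
- Between groups, unaveraged: the same power "within each condition of 1.25 standard deviations".

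It does not state alpha, sidedness, the test, which SD is meant, the number of conditions, or the correlation between a person's repeated ratings.

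Section V, items 3 and 5 set out four groups of 15: lean controls, obese non-diabetic, T2DM and T1DM (for example "15 T1DM subjects who will be age and BMI matched to control, non-diabetic subjects"). Section VII, item 1 gives the total as "targeted for enrollment at Yale for this protocol 60", which is 4 × 15. The Research Plan (Section V, item 3) has each participant wear the monitor once, for up to 7 days of ordinary life, while keeping a food record with hunger before and fullness after meals. Clamp-controlled glucose levels appear only in the Background, in the account of the group's earlier work.

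**The concern.** A main effect of group across conditions is a repeated-measures quantity. Each person's scores are averaged over conditions, the averaging removes some within-person noise, and a smaller difference becomes detectable. That is the natural reason for 1.0 SD across conditions to sit beside 1.25 SD inside one condition. In a study with no conditions, the reason for the smaller figure disappears.

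Item 12 is the only statistical text in the plan, so it is what a reader will use to judge an inconclusive group comparison. If 1.0 SD is believed to be detectable with at least 80% power when the true figure may be 59% to 75%, a null result will seem to rule out more than it does. The pilot label limits the consequence but does not make the stated power correct.

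**Working it through.** **Inputs.** From the documents: n = 15 per group, 4 groups, 60 in total, and stated effects of 1.1, 1.0 and 1.25 SD. Assumed: two-sided alpha 0.05, one analysed value per participant, equal SDs, all 15 per group evaluable.

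**1. The plan's within-group figure (1.1 SD).** The paired t test has noncentrality d√15 on 14 df, where d is in units of the SD of the change. Power of 80% is reached at d = 0.778. If the unit is instead the SD of a single rating, with correlation ρ between a person's two ratings, the detectable difference is 0.778 × √(2(1 − ρ)). At ρ = 0 this is 0.778 × 1.414 = 1.100, and power at 1.1 SD is 79.98%. The plan's figure therefore reproduces. If 1.1 were in units of the SD of the change, power would be 97.7%.

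**2. The plan's 1.25 SD figure.** Two-sample t test: 91.0%. Four-group F test with the two extreme groups 1.25 SD apart and the other two midway: 80.1%. The stated power is met either way.

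**3. The 1.0 SD figure, one pair of groups.** Noncentrality is 1.0 × √(15/2) = 2.739 on 28 df, giving power of 75.3%. The normal approximation gives 78.2%; using the error variance pooled over all four groups gives 76.8%. The detectable difference at 80% is 1.06 SD, and 80% power at 1.0 SD would need 17 per group.

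**4. The 1.0 SD figure, overall four-group test.** F test on 3 and 56 df, with noncentrality λ = 15 × Σ(μᵢ − μ̄)² in SD units and a 1.0 SD gap between the extreme groups:

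| Pattern of the four means | Σ(μᵢ − μ̄)² | λ | Power at 1.0 SD | Range for 80% power |
|---|---|---|---|---|
| Two extremes, two midway | 0.500 | 7.50 | 58.9% | 1.25 SD |
| Equally spaced | 0.556 | 8.33 | 64.0% | 1.18 SD |
| One group apart from three | 0.750 | 11.25 | 78.3% | 1.02 SD |
| Two against two | 1.000 | 15.00 | 89.6% | 0.88 SD |

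Only the last pattern reaches 80%.

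**5. What averaging would need to supply.** Averaging m ratings with correlation ρ multiplies the variance by (1 + (m − 1)ρ)/m. In single-rating SD units, 1.0 SD reaches 80% power when this factor is at most:

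- (1/1.060)² = 0.89 for one pair, that is ρ up to about 0.78, 0.84 or 0.85 for m = 2, 3 or 4;
- (1/1.249)² = 0.64 for the four-group test with two groups midway, that is ρ up to about 0.28, 0.46 or 0.52.

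The plan gives neither m nor ρ.

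**The case against.** The strongest reply is that item 12 is ordinary repeated-measures wording and that its two between-group figures fit together. The 1.25 SD figure matches the four-group test almost exactly, and 1.0 SD follows from averaging over a few conditions at moderate correlation; for a single pair, averaging works over a wide range of correlations. As arithmetic, this stands. It does not help here, because the Research Plan supplies no conditions. Categories could be built from the glucose trace, or meal ratings averaged over the week, but the plan describes neither.

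Other routes to 80% exist. A one-sided 0.05 test gives 84.8% for one pair, but no sidedness is stated. Age and BMI matching could help two of the pairs (T2DM with obese, T1DM with lean): if people were matched individually and analysed as pairs, an assumed within-pair correlation of 0.2 gives 81%. The documents do not say that the matching is individual or that the analysis would use it, and it would not cover the other group comparisons.

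It is also fair that the pairwise shortfall is modest: 75% against 80%, or 17 rather than 15 per group.

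A reader might infer more than the documents support. One inference is that the power figures as a whole fail to reproduce; in fact 1.1 SD and 1.25 SD both do. Another is that 0.78 SD should replace 1.1 SD as a correction; the two are one calculation in different units. A third is that attrition will cut power further. Enrolment leaves no margin over 4 × 15, but the documents give no loss rate, so any such figure is an assumption.

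**Conclusion.** The point holds for the 1.0 SD figure. Given one value per person, 15 evaluable per group and two-sided 0.05, at least 80% power is not delivered for a single pair (75%), and it is delivered for the four-group test in only one of the four patterns examined (59%, 64%, 78% and 90%). In the study as described, 1.0 SD and 1.25 SD are two figures for one contrast, and the larger is the one that meets its claim.

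The conclusion depends on the assumed alpha and on reading the SD as that of the participant-level value. If the SD meant is that of a single rating and several meal ratings per person are averaged, 1.0 SD could be supported, but only once the plan says so and gives the number of ratings and the within-person correlation. The 1.1 SD within-group figure has 80% power to rounding if it refers to single, uncorrelated ratings and 98% if it refers to the change, so it needs only its SD named. This is worth correcting and does not threaten the study.

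**What to change.** Delete the reference to glycemic conditions from Section V, item 12 and replace the three figures with text such as:

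> With 15 evaluable participants per group (two-sided 0.05), there is 80% power for a two-group difference of 1.06 SD of the participant-level value, for 1.25 SD between the widest pair in the overall four-group test (other groups midway), and for a within-group change of 0.78 SD of the change.

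State how the participant-level value is formed. If it averages repeated meal ratings and the power is to be quoted in single-rating units, add the assumed number of ratings and within-person correlation. Optionally add the two-group figure with fewer evaluable people, labelled as an assumption: 1.15 SD with 13 per group, 1.20 SD with 12 (power at 1.0 SD 69% and 65%).

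The cost is protocol wording. The between-group figure becomes slightly less favourable, and no participants or procedures are added.
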